9.2.4 Tertiary/exploratory endpoint(s) analyses

Unless otherwise noted, tertiary and exploratory endpoints will be summarized through appropriate descriptive methods, according to the type of endpoint.

9.2.4.1 Analysis of biomarkers

For exploratory parameters that include biomarkers, summarized description by intervention group and timepoint, if applicable will be provided. Absolute and percent change from baseline will be calculated for selected parameters. Time profile plots (mean +/- SEM, SD) will be presented for selected parameters by intervention group.

9.2.5 Multiplicity adjustment

Multiplicity is considered for the significance testing of multiple efficacy endpoints. The overall Type-I error rate will be controlled at the 2-sided 0.05 level.

As a nonbinding futility IA is planned for the study (see [Section 9.3](#)), an administrative penalty of $\alpha = 0.001$ will be taken from the significance level used at final analysis; that is, a 2-sided $\alpha = 0.049$ will be used for the final primary efficacy analysis. No further multiplicity adjustment will be performed for the IA.

At the final analysis, the family-wise Type I error rate for testing multiple hypotheses pertaining to the primary endpoint and secondary endpoints will be strongly controlled using a gate-keeping procedure. The procedure starts with testing the co-primary endpoints between 300 mg Q2W and placebo at the 2-sided 0.049 significance level. If both co-primary endpoints are significant, then the co-primary endpoints for 300 mg Q4W, the key secondary endpoints and a selective set of secondary endpoints including the efficacy endpoints on asthma and AERD sub-populations for both doses will be tested using a prespecified multiplicity testing procedure with the overall Type I error rate being controlled at 0.049 level among the multiple endpoints and the comparisons between each dose (300 mg Q2W or 300 mg Q4W) and placebo. The complete list of the endpoints and the multiplicity testing procedure will be specified in the SAP.

9.2.6 Safety analyses

All safety analyses will be performed on the safety populations. The summary of safety results will be presented by intervention group.

9.2.6.1 Adverse events

General common rules for adverse events

The AEs will be analyzed in the following 3 categories:

- Pre-treatment AEs: AEs that developed, worsened or became serious during the pre-treatment period.
- TEAEs: AEs that developed, worsened or became serious during the treatment-emergent period.
- Post-treatment AEs: AEs that developed, worsened or became serious during the post-treatment period.

Similarly, the deaths will be analyzed in the pre-treatment, TE and post-treatment periods.

Analysis of all adverse events

Adverse event incidence table will be provided by treatment group for all types of TEAEs: all TEAEs, all treatment emergent AESI (defined with a preferred term [PT] or a prespecified grouping), all treatment-emergent SAEs and all TEAEs leading to permanent treatment discontinuation.

The AE summaries will be generated with number (%) of participants experiencing at least 1 event.

Deaths will also be analyzed.

9.2.6.2 Laboratory variables, vital signs and electrocardiograms

Quantitative analyses

When relevant, for laboratory variables, vital signs and ECG variables, descriptive statistics for results and changes from baseline will be provided for each planned visit, the last value and the worst value (minimum and/or maximum value depending on the parameter) during the on-treatment period. These analyses will be performed using central measurements only (when available) for laboratory variables.

Analyses according to Potentially Clinically Significant Abnormality

PCSA analyses will be performed based on the PCSA list currently in effect at Sanofi at the time of the database lock.

Analyses according to PCSA will be performed based on the worst value during the TE period, using all measurements, either scheduled, nonscheduled or repeated.

For laboratory variables, vital signs and ECG variables, the incidence of participants with at least 1 PCSA during the TE period will be summarized regardless of the baseline level and according to the following baseline status categories:

- Normal/missing.
- Abnormal according to PCSA criterion or criteria.

For ECG, the incidence of participants with at least one abnormal ECG during the TE period will be summarized regardless of the baseline level and according to the following baseline status categories:

- Normal/missing.
- Abnormal.

9.2.6.3 Product complaints

Product complaints will be summarized in the safety population.

9.2.7 Other analyses

Analyses of PK and immunogenicity will be described in the SAP.

For a regional or national emergency declared by a governmental agency, contingency measures are included in Appendix 9 ([Section 10.9](#): Contingency measures for a regional or national emergency that is declared by a governmental agency).

9.3 INTERIM ANALYSES

A non-binding futility interim analysis (IA) will be planned after a minimum of approximately 90 pooled participants in the Phase 3 studies (EFC18418 and EFC18419) have completed at least a minimum of 24 weeks. There is no plan to change the conduct of this trial except to possibly stop the trial due to unfavorable benefit-risk. The unblinded interim look will be performed by an independent group separated from personnel involved in the trial conduct, data collection and management, and final statistical analysis.

A detailed IA plan will be finalized, including the decision rules, analyses to be included, methods to be used, and the processes and procedure intended to control access to comparative interim results to preserve trial integrity, prior to any interim administrative look.

An administrative penalty of 0.001 will be taken from the significance level used at final analysis, if applicable.

Data Monitoring Committee

This study will use an independent DMC. Details on DMC structure and role are presented in [Section 10.1.5](#).

During the course of the study, an external statistician (independent from the Sponsor) will perform the unblinded safety and efficacy analyses for the purpose of the DMC data review and formal non-binding futility IA. Access to the data and analyses will be restricted to the DMC members. In addition, following the formal non-binding futility IA, DMC will make recommendations on continuation of the study, and will communicate unblinded results to limited personnel from the Sponsor, only if criteria pre-specified by the Sponsor are met. Access to the data and analyses will be provided to limited personnel from the Sponsor involved in the conduct of the study, if applicable. There is no plan to change the conduct of this trial except to possibly stop the trial due to unfavorable benefit-risk.

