6.4 BLINDING

This is a double-blind study in which participants/care providers/Investigators/outcomes assessors are blinded to study intervention. The IRT will be programmed with blind-breaking instructions. In case of an emergency, the Investigator has the sole responsibility for determining if unblinding of a participant's intervention assignment is warranted (eg, in case of available antidote). Participant safety must always be the first consideration in making such a determination. If the Investigator decides that unblinding is warranted, he/she may, at the Investigator's discretion, contact the Sponsor to discuss the situation prior to unblinding a participant's intervention assignment unless this could delay emergency treatment for the participant. If a participant's intervention assignment is unblinded, the Sponsor must be notified within 24 hours of this occurrence. The date and reason for the unblinding must be recorded.

The bioanalyst and pharmacokineticist responsible for the sample analysis and PK evaluation will be unblinded. They will, however, agree not to disclose the randomization schedule or the individual unblinded analytical results before the database lock.

Sponsor safety staff may unblind the intervention assignment for any participant with an SAE for the purpose of expedited regulatory reporting (see [Section 8.4.4](#)). Sponsor staff involved in the conduct of the study will remain blinded to the participant intervention assignment.

Methods of blinding

Itepekimab and placebo will be provided in identically matched 2-mL PFS. To protect the blind, each treatment kit of 2-mL (itepekimab/placebo) glass PFS will be prepared such that the treatments (itepekimab and its matching placebo) are identical and indistinguishable and will be labeled with a treatment kit number.

In accordance with the double-blind design, study participants, Investigators, and study site personnel will remain blinded to study treatment and will not have access to the randomization scheme or to the IMP content (itepekimab or placebo) except under circumstances described above in this section.

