10.1.5 Committees structure

10.1.5.1 Data Monitoring Committee

A DMC, independent from the Sponsor, will be monitoring this study. This committee is governed by a DMC Charter. The DMC will comprise externally based individuals with expertise in the diseases under study, biostatistics, or clinical research. The composition of the committee is dependent upon the scientific skills and knowledge required for monitoring the particular study.

The primary responsibilities of the DMC are to review safety data, and efficacy where needed, during the course of the trial for evaluation of benefit/risk, review results, and make appropriate recommendations to the Sponsor regarding the stopping of a study for efficacy, for safety, or for futility. DMC recommendation may also include modifications of the study or discontinuing individual participants or specific subgroups of participants. In the above-mentioned capacities, the DMC is advisory to the Sponsor. The Sponsor is responsible for promptly reviewing and for taking into account in a timely manner the recommendations of the DMC in terms of study continuation with or without alterations, or of potential termination of a dose or study.

- Case unblinding may be performed for above reviews if necessary.

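### Section 9.3 opens unblinded interim data to Sponsor staff who run the study, against its own DMC-only access rule and the blinding rule in Section 6.4

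*Protocol*

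**What the plan says.** **Who sees interim results.** Protocol Section 9.3 contains four statements:

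- On who does the work: "The unblinded interim look will be performed by an independent group separated from personnel involved in the trial conduct".
- On access, in the Data Monitoring Committee paragraph: "Access to the data and analyses will be restricted to the DMC members". The preceding sentence has an external statistician run the analyses.
- On release after the futility look, the DMC "will communicate unblinded results to limited personnel from the Sponsor, only if criteria pre-specified by the Sponsor are met".
- Directly after that: "Access to the data and analyses will be provided to limited personnel from the Sponsor involved in the conduct of the study, if applicable".

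Section 6.4 states: "Sponsor staff involved in the conduct of the study will remain blinded to the participant intervention assignment". Its exceptions are the bioanalyst and pharmacokineticist, Sponsor safety staff handling expedited SAE reports, and emergency code breaks by the Investigator.

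**What the look may lead to.** Section 9.3 plans one non-binding futility analysis, after a minimum of about 90 participants pooled over EFC18418 and EFC18419 have completed 24 weeks. It says: "There is no plan to change the conduct of this trial except to possibly stop the trial due to unfavorable benefit-risk". Section 9.2.5 takes 0.001 off the final significance level, leaving a two-sided 0.049, and makes no other adjustment for the interim. Section 10.1.5.1, to which Section 9.3 refers for the DMC's role, includes "recommendations to the Sponsor regarding the stopping of a study for efficacy, for safety, or for futility".

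**The concern.** A site monitor or study manager reading Section 6.4 expects to stay blinded. The same person reading the last access sentence of Section 9.3 is a possible recipient of unblinded data. An interim analysis plan written under this protocol cannot satisfy both.

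The stake is operational bias. Staff who run the study influence how sites are managed and how deviations are handled. Section 7.1.1 also allows withdrawal from treatment at the Sponsor's request, or at the Sponsor's discretion after a protocol deviation. The look may come early: the minimum is about 90 participants over two studies, and this study alone plans about 210. Much Week 24 data could therefore still be outstanding. Because the look pools the studies, a leak would reach EFC18419 as well.

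The secondary stake is type I error. A DMC that may recommend stopping for efficacy, without a stated boundary, could act at a level that the 0.001 deduction does not cover.

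**Working it through.** **1. The access rules compared**

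| Source | Who may see unblinded interim material | Condition |
|---|---|---|
| 9.3, first paragraph | The look is performed by a group apart from trial conduct | None |
| 9.3, DMC paragraph | DMC members only | None |
| 9.3, next sentence | Limited Sponsor personnel, function not stated | Sponsor's pre-specified criteria met |
| 9.3, sentence after that | Limited Sponsor personnel who take part in study conduct | If applicable |
| 6.4 | Sponsor staff who take part in study conduct stay blinded | Listed exceptions, none covering this access |

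Row 2 cannot hold together with row 3 or row 4 unless an exception is written into it. Row 4 conflicts with row 5 because both describe the same group. Row 3 alone would be compatible with row 5 if the recipients had no conduct role, so the wording that breaks the firewall is in row 4. The pre-specified criteria appear only in row 3, which concerns results. Row 4 covers data and analyses and carries only the weaker condition.

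**2. The plan's own figures**

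Inputs from Sections 9.2.5 and 9.4: overall two-sided alpha 0.05, deduction 0.001, 70 per arm, NPS difference 1.10 with SD 1.79, NCS difference 0.55 with SD 0.9.

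- Final alpha: 0.05 − 0.001 = 0.049. This matches.
- Standard error = SD × √(2/70). NPS: 1.79 × 0.1690 = 0.303. NCS: 0.9 × 0.1690 = 0.152.
- Power at two-sided 0.049 by noncentral t with 138 df: NPS 95.0%, NCS 94.8%. The normal approximation gives 95.2% and 95.0%. The stated figure is 95% for each.
- Smallest significant difference: NPS 0.601, NCS 0.302. The stated figures are about 0.60 and 0.30.
- Combined power with independent endpoints: 0.95 × 0.95 = 0.9025. The stated figure is at least 90%.

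None of these depends on who sees the interim results.

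**3. What an efficacy stop would do**

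Take one interim test at two-sided level a₁ and a final test at 0.049, with critical values c₁ and c₂ and correlation √t, where t is the information fraction. Then

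total type I error = 1 − P(|Z₁| < c₁ and |Z₂| < c₂).

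The size of EFC18419 is not given, so t is an assumption. If it also has 210 participants, t = 90/420 = 0.214. The range shown is 0.1 to 0.5.

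| Interim level a₁ | t = 0.1 | t = 0.214 | t = 0.5 |
|---|---|---|---|
| 0.001 | 0.0498 | 0.0496 | 0.0492 |
| 0.01 | 0.0576 | 0.0566 | 0.0536 |
| 0.049 | 0.0930 | 0.0900 | 0.0815 |

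The deduction covers an efficacy stop at p < 0.001, since 0.001 + 0.049 = 0.05 is an upper bound. It does not cover one at 0.01 or 0.049. The table is for one endpoint and one dose comparison. Requiring both co-primary endpoints would lower the values.

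**The case against.** The best defence has four parts.

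- **Access is conditional.** It is limited in number, tied to pre-specified criteria in the sentence before, and subject to an interim analysis plan that Section 9.3 promises will control access. This stands as far as frequency goes: release is not routine. It does not cure the text, because the conditions govern when and how many, and the recipients are still described as conduct staff.
- **The neighbouring sentences have different scope.** The independent-group sentence governs who performs the look, and Section 6.4 protects individual treatment assignment, whereas interim output may be summaries by arm. This partly stands. However, Section 9.3 speaks of data as well as analyses, and its DMC-only sentence concerns exactly the same material.
- **The harm is bounded.** A reader might infer that both co-primary comparisons would be compromised beyond repair. The documents do not support that. Participants, Investigators and outcome assessors stay blinded (6.4), NPS is read centrally by independent reviewers (8.2.2), and NCS comes from the participant's own diary (8.2.1, 8.2.3).
- **Stopping for efficacy is general committee language.** The phrase is only in Section 10.1.5.1, and the committee is advisory. The synopsis has it review efficacy to weigh benefit against risk. A reader might infer that the interim section itself licenses an efficacy stop, or that repeated looks at 0.049 are planned and alpha is inflated accordingly. Neither follows: Section 9.3 plans one futility look and no efficacy test. What remains is a phrase that does not match the alpha plan.

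**Conclusion.** The main point holds. Section 9.3 conditionally opens unblinded interim data and analyses to Sponsor staff who run the study, contradicting its own DMC-only rule and Section 6.4. The consequence is a risk of operational bias in this study and in EFC18419. Its size cannot be computed from the protocol, and it arises only if release occurs under the text as written. It deserves correction before the look because the protection cannot be restored once those staff have seen results.

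The efficacy-stopping phrase in Section 10.1.5.1 is a secondary inconsistency. The stated alpha, sample size and power are right and stay as they are. Type I error could exceed 0.05 only through an efficacy stop at a level looser than 0.001. For one endpoint and one comparison, with an assumed information fraction of 0.1 to 0.5, the total would be about 0.054 to 0.058 at interim p < 0.01 and 0.082 to 0.093 at p < 0.049. The protocol plans no such stop, so these figures show why the phrase should go. They do not describe the error rate of the trial as planned.

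**What to change.** - **Section 9.3, last access sentence:** state that recipients are limited Sponsor personnel *not* involved in running the study, that they are identified in the interim analysis plan before the look, and that they receive material only if the pre-specified criteria are met. Because the look pools both studies, the same exclusion should cover EFC18419.
- **Section 9.3, DMC-only sentence:** name the exceptions, namely the independent statistician and the conditional Sponsor group above, so that the access rules agree with each other and with Section 6.4.
- **Section 10.1.5.1:** delete efficacy from the list of grounds for recommending a stop, so that the remit matches Sections 9.2.5 and 9.3. Check the DMC Charter for the same phrase.

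The cost is a few wording changes in the protocol, carried into the interim analysis plan and, if needed, the charter. No participants or analyses are added, and alpha, sample size and power do not change. The edits must be in force before the interim look.

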9.4 SAMPLE SIZE DETERMINATION

Approximately 210 participants will be randomized in 1:1:1 ratio to investigational intervention groups.

The sample size calculations are based on the co-primary endpoints NPS and NCS. The planned sample size is approximately 70 participants per study intervention group. With a two-sample t-test at a two-sided significance level of $\alpha = 0.049$, this sample size will provide:

- 95% power to detect a -1.10 difference for change from baseline in NPS at Week 24 between itepekimab and placebo and a common SD of 1.79. The minimal detectable difference is around -0.60.
- 95% power to detect a -0.55 difference for change from baseline in NCS at Week 24 between itepekimab and placebo and a common SD of 0.9. The minimal detectable difference is around -0.30.

The combined power of the 2 co-primary efficacy endpoints is at least 90% assuming no negative correlation between the 2 endpoints.

Differences of -1.10 and -0.55 in NPS and NCS from placebo are considered clinically relevant (54). The common SDs were estimated from LIBERTY NP SINUS-24 and SINUS-52 trials with dupilumab (NCT02912468; NCT02898454).

For the key secondary endpoints of change from baseline in NPS and NCS at Week 52, the study will have a 95% power to detect the same treatment differences as for the co-primary endpoints with the same assumed common SDs based on a two-sided α level of 0.049.

Note that as the primary analyses will be performed based on the ITT population with the dropouts (ie, one of the intercurrent events) handled using the treatment policy strategy and missing data imputed using the MI method, the sample size calculations were performed on all randomized participants. In other words, the detectable treatment differences stated above are for ITT population including early dropouts. Very low dropout rates (<5%) were observed from LIBERTY NP SINUS-24 and SINUS-52 studies (NCT02912468; NCT02898454), therefore the impact on the treatment effects is expected to be minimal.

Calculations were made based on two-sample t-test using nQuery Advisor 9.2.1.0.

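### Section 9.4's 95% power for the Week 52 key secondaries is stand-alone power; under the gatekeeping in 9.2.5 the chance of declaring one significant is about 85–90%, and about 83–86% for the Q4W co-primary pair

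*Protocol*

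**What the plan says.** Protocol section 9.4 sizes the trial on the two Week 24 co-primaries. "Approximately 210 participants will be randomized in 1:1:1 ratio to investigational intervention groups", and "The planned sample size is approximately 70 participants per study intervention group". The method is given as "With a two-sample t-test at a two-sided significance level of" 0.049. The NPS result is "95% power to detect a -1.10 difference for change from baseline in NPS at Week 24 between itepekimab and placebo and a common SD of" (the SD being 1.79), and the NCS result is "95% power to detect a -0.55 difference for change from baseline in NCS at Week 24 between itepekimab and placebo and a common SD of" (the SD being 0.9). For the pair, section 9.4 adds: "The combined power of the 2 co-primary efficacy endpoints is at least 90% assuming no negative correlation between the 2 endpoints". None of these sentences says which of the two itepekimab regimens is meant.

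For Week 52 the same section continues: "For the key secondary endpoints of change from baseline in NPS and NCS at Week 52, the study will have a 95% power to detect" effects equal to those at Week 24, with the same SDs and the same two-sided 0.049.

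Section 9.2.5 fixes the order of testing. The two co-primaries for 300 mg Q2W versus placebo come first, at 0.049. "If both co-primary endpoints are significant, then the co-primary endpoints for 300 mg Q4W, the key secondary endpoints and a selective set of secondary endpoints" are tested, for both doses, with 0.049 controlled across all of them together. The order and any split of alpha after the first step are left to the SAP.

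**The concern.** The two sections describe different events. Section 9.4 gives the chance that one comparison, taken alone, reaches p < 0.049. Section 9.2.5 allows a Week 52 endpoint, or anything for Q4W, to be declared significant only if two earlier tests have both succeeded. A test placed behind another step cannot succeed more often than that step is passed, and section 9.4 itself puts that probability at about 90%. A flat 95% for the Week 52 endpoints therefore lies above the limit implied by the sentence on combined power in the same section.

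The missing dose label has a similar effect. The 90% for the co-primary pair is right for Q2W, which is tested first. The Q4W pair needs four successes instead of two.

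At stake is what the sponsor, ethics committees and regulators take the protocol to promise about the Week 52 durability claims and the Q4W regimen. The size of the trial is not at stake.

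**Working it through.** **Inputs from section 9.4:** n = 70 per arm; two-sided alpha 0.049; NPS difference 1.10 with SD 1.79; NCS difference 0.55 with SD 0.9; the same values at Week 52. **From section 9.2.5:** both Q2W co-primaries must be significant before anything else is tested.

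**Step 1: reproduce the printed figures.** For a two-sample t-test with 138 df, the critical value is 1.986 and the noncentrality is (difference/SD) × √(70/2).
- NPS: (1.10/1.79) × √35 = 0.6145 × 5.916 = 3.636, power 94.96%.
- NCS: (0.55/0.9) × √35 = 0.6111 × 5.916 = 3.615, power 94.75%.
- Smallest significant difference, 1.986 × SD × √(2/70): 0.601 and 0.302 (stated: about 0.60 and 0.30).
- Both co-primaries under independence: 0.9496 × 0.9475 = 89.98% (stated: at least 90%).

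Every printed figure reproduces as a stand-alone calculation.

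**Step 2: the ceiling.** For any Week 52 or Q4W endpoint, P(declared significant) ≤ P(both Q2W co-primaries significant). That bound is 89.98% under independence. It can never exceed the smaller of the two marginal powers, 94.75%, even with perfectly correlated endpoints. No choice made after the first step can raise it.

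**Step 3: gated power under independence, full 0.049 passed on.** For one Q2W Week 52 endpoint:
- NPS: 0.9496 × 0.9475 × 0.9496 = 85.4%.
- NCS: 0.9496 × 0.9475 × 0.9475 = 85.3%.

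**Step 4: gated power with correlation.** The protocol gives no correlations, so these are assumed: NPS–NCS 0 to 0.7; Week 24–Week 52 0 to 0.9; cross-correlations as the product of the two. Between-dose correlation is 0.5, from the shared placebo arm with 1:1:1 allocation. Correlated t statistics were simulated with 600,000 draws per full-alpha scenario and 200,000 per half-alpha scenario. The table shows NPS; NCS differs by at most 0.6 percentage points.

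| NPS–NCS corr. | Wk 24–52 corr. | Pass first step | One Q2W Wk 52 endpoint, full 0.049 | Q4W co-primary pair, full 0.049 | Q2W Wk 52, 0.0245 | Q4W pair, 0.0245 |
|---|---|---|---|---|---|---|
| 0 | 0 | 0.900 | 0.854 | 0.827 | 0.822 | 0.766 |
| 0.3 | 0.5 | 0.904 | 0.868 | 0.836 | 0.840 | 0.784 |
| 0.5 | 0.7 | 0.910 | 0.882 | 0.845 | 0.853 | 0.793 |
| 0.7 | 0.9 | 0.917 | 0.901 | 0.857 | 0.877 | 0.813 |

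The 0.0245 columns illustrate a half split; the protocol states no split. At an NPS–NCS correlation of 0.99, which is not realistic, the first step is passed with probability 0.94, one Q2W Week 52 endpoint reaches at most 0.923, and the Q4W pair reaches about 0.895.

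**Step 5: power once the first step has been passed, full alpha.** Divide by the pass probability.
- Q2W Week 52 NPS: 0.854/0.900 = 0.949 to 0.901/0.917 = 0.983.
- Q4W co-primary pair: 0.827/0.900 = 0.919 to 0.857/0.917 = 0.935.

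**The case against.** The strongest reply is that nothing is miscalculated. Section 9.4 names its test and its alpha, every number reproduces, and marginal power per comparison is a common convention. This stands: the point is not an arithmetic error. It does not dispose of the matter, because section 9.4 presents the 95% as power the study will have and nowhere calls it nominal or ungated. The same section does report joint power for the co-primary pair, and stops one step short of the endpoints behind it.

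A second reply is that the post-gatekeeping procedure belongs to the SAP. This also stands for the order, recycling and split of alpha, whose absence is no fault here. But the first step is already fixed in 9.2.5, and the ceiling in step 2 follows from that alone.

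A reader might go further and infer that the trial has a 10–15% risk of missing a true Week 52 effect, so that a negative Week 52 or Q4W result would be hard to interpret. The documents do not support that. Most of the shortfall (8–10 points) is failure of the first step, in which case these hypotheses are not formally tested at all. Once it is passed, and with full alpha, power is about 95–98% for a Q2W Week 52 endpoint and about 92–93% for the Q4W pair, in line with or above the printed values. Nor may a reader conclude that 210 participants are too few: the sample size rests on the Q2W co-primaries, whose power is as stated.

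Finally, the gated figures use the same t-test as section 9.4 and assumed correlations. They share its simplifications and should be read as ranges.

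**Conclusion.** The point holds as a stated power that is inconsistent with the testing procedure. The 95% for each Week 52 key secondary is correct only as stand-alone per-comparison power at two-sided 0.049. The co-primary figure of at least 90% is correct only for 300 mg Q2W.

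Under 9.2.5, the probability of declaring a Week 52 key secondary significant is capped at about 90% (independence) to 92% (NPS–NCS correlation 0.7). With full alpha passed on, it is about 85–90% for one Q2W Week 52 endpoint, 5 to 10 points below the printed figure. The Q4W co-primary pair has about 83–86%, some 4 to 7 points below 90%. With alpha halved after the first step, the ranges fall to about 82–88% and 77–81%.

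The cap follows from the protocol's own inputs plus the NPS–NCS correlation; the other ranges also depend on the assumed Week 24–Week 52 correlation and post-gatekeeping alpha. The correction is worth making because it is cheap and concerns a figure readers rely on.

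**What to change.** Change section 9.4 only:

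1. Label the 95% for the Week 52 key secondaries as nominal power per comparison at two-sided 0.049, before the gatekeeping procedure is taken into account.
2. State that the co-primary figures, including the combined power of at least 90%, apply to 300 mg Q2W versus placebo.
3. Add the power under the gatekeeping procedure for the Week 52 key secondaries and for the Q4W co-primary pair, printing the assumed NPS–NCS and Week 24–Week 52 correlations and the alpha assumed after the first step. For example: about 85–90% for one Q2W Week 52 endpoint and about 83–86% for the Q4W pair, with full 0.049 passed on, NPS–NCS correlation 0–0.7 and Week 24–Week 52 correlation 0–0.9; lower if alpha is split.
4. Note that none of these can exceed the probability that both Q2W co-primaries are significant.

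Keep N = 210 and the testing procedure as they are. The cost is a few sentences and somewhat less favourable printed figures; no participants are added and no analysis changes.
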